At least half the days in the past 6 months	1
Less than half the days in the past 6 months	2

4. In the past 7 days, how would you rate your low back pain on average?" (with an accompanying description of the following numerical pain intensity scale:

No pain	0	1	2	3	4	5	6	7	8	9	10	Worst imaginable pain
---------	---	---	---	---	---	---	---	---	---	---	----	-----------------------

Titration, Treatment and Tapering Periods Beginning with Week 1, patients will receive study medication for eight weeks after which they will be tapered off of investigational treatments (Figure 1). Study visits will take place at the UCSD Center for Medicinal Cannabis Research.

Figure 1 Study Visits

Outcome measures will be collected during the six study visits, represented above as red vertical arrows. Driving simulation will be performed on the Hillcrest Campus at times denoted by the blue X's

Subjects will be randomly assigned to receive either one active study medication (e.g., medium-strength vaporized cannabis, or dronabinol) plus one placebo study medication, or double-placebo. Within the limits of safety and tolerability, patients will undergo titration of both vaporized and oral study medication during Weeks 1-4. The oral medication will be titrated from a minimum of 5 mg qd up to a maximum of 10 mg tid. The vaporized cannabis will be titrated from a minimum of 4 puffs to a maximum of 18 puffs per day. The aforementioned falls within the parameters of consumption of cannabis as depicted in a survey of medicinal cannabis patients.⁸ The dosing, in terms of the maximum number of puffs at each vaporization session, will also be consistent with the amount utilized in our previous human laboratory experiment.³ Subjects not able to tolerate the minimum amounts described above by the end of Week 4 will be dropped from the study and replaced by another volunteer. Subjects will be informed that concurrent medications should be administered on a continuing basis during the study at a constant amount and frequency.

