During treatment at home, patients will maintain a paper daily diary to record their intake of vaporized cannabis (i.e., number of vaporization sessions, puffs), oral study medications, and breakthrough pain medications, as well as pain relief measurements. In order that an effect from study medication will be evident, subjects will be asked to enter data into paper diary within a one-to-two hour window following dosing of study and breakthrough medications. In between visits, patients

will be contacted by telephone every 7 days so that the investigative team can discuss compliance and answer any questions (Appendix 5).

Study Visits:

Subjects will come in for 2-hour study visits at the intervals designated by the vertical arrows in Figure 1. A review of the paper daily diary, and, after the baseline week, the completion of the assessments described below under Outcome Measures will also be reviewed.

Study Δ9-THC will be packaged in separate prescription vials for each vaporization session to be performed at the subject's residence. The vial will be marked with the date, directions for timing of vaporization session(s), and the maximum number of puffs from that vial. The collection vial will also be labeled for return of vaporized cannabis. All study medication will be packaged in a security container for purposes of preventing diversion with instructions to keep the locked strong box in a secure location. At the time of the subsequent visit, the vaporized and unused cannabis will be weighed by the research pharmacist who will report any suspected lapse of safekeeping of cannabis to the PI. Table 1 below outlines the amount of vaporized and oral study medication participants will be administered throughout the study.

Table 1 Schedule of Administration of Vaporized and Oral Study Medication

week	maximum dronabinol 5 mg or placebo tablets	maximum dronabinol 5 mg or placebo tablets per week	number of vaporization sessions per day	maximum number of puffs per day	number of 400 mg vials per week (8 puffs per vial)
Screening					
Baseline					
1	1 po qd	7	1	4	4
2	1 po bid	14	2	8	7
3	1-2 po tid	28	3	12	11
4	2 po tid	42	3	18	16
5	2 po tid	42	3	18	16
6	2 po tid	42	3	18	16
7	2 po tid	42	3	18	16
8	2 po tid	42	3	18	16
Taper Week 1	1 po tid	21	2 (average)	9	10
Taper Week 2	1 po qd	7	1 (average)	4	4

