- Preventing children and adolescents from gaining access to medicinal cannabis because of potential harm to their well-being. Subjects will be required to store cannabis in an area of their home that would prevent anyone else from discovering its location.
- Because some people cannot control their use of cannabis, we will not allow patients with recent substance abuse histories (less than 12 months) to participate.
- We will exclude patients if they are pregnant or refuse to exercise birth control if engaging in sexual activities that could result in pregnancy, have a heart disease or heart rhythm problem or have a history of serious mental illness (e.g., schizophrenia, mania, or a history of hallucinations or delusions)
- In order to avoid carcinogens, we will have subjects use a vaporizer rather than smoke joints or use a water pipe.

- We will instruct subjects not to drive a car or operate heavy machinery for 3-4 hours after use of medicinal cannabis, or longer if larger doses are used or the effects of impairment persist. They will use a designated driver for automobile transportation if they have to go out sooner than 3-4 hours after taking this medicine.
- As the response to cannabis varies widely, participants will titrate to effect and in essence use the minimum amount of medicinal cannabis needed to obtain relief from pain.
- A cannabis withdrawal syndrome will be under surveillance for two weeks; difficulty with getting to sleep and angry outbursts might require that they withdraw from the cannabis more slowly.

The UCSD Department of Psychiatry (Appendix 17) is committed to providing the resources and other supports (e.g., data management and information systems, statistical, and physical performance site) to ensure the timely implementation, conduct, and completion of this program.

Data and Safety Monitoring Board (DSMB)

A DSMB will be selected utilizing a group of experts that will advise the study investigators, with the primary responsibility to monitor human subject safety. The members will be comprised of at least 3 independent clinicians familiar with the conduct of clinical trials. The DSMB will consider study-specific data as well as relevant background information about the test agents and target population under study. The DSMB will review the protocol, including the safety monitoring plan, and identify any major concerns prior to implementation. During the trial the DSMB will review:

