Dronabinol and Vaporized Cannabis in Chronic Low Back Pain

Statistical analysis plan

Principal investigators:

**[name].
[name]. (retired)**

Protocol Statisticians:

**[name].
[name].**

April 24, 2020

1. Summary of Study Design

This study is a prospective, randomized, placebo controlled, double blind, phase 2/3 clinical trial of dronabinol and vaporized cannabis for the treatment of chronic low back pain. A total of 120 (n = 120) subjects with chronic low back pain, aged between 19-70 years will be randomized in a ratio of 1:1:1 to the three treatment arms (40 participants per arm): 1) vaporized 3.7% Δ9-THC /5.6% cannabidiol plus placebo oral pills, 2) oral Δ9-THC (dronabinol) plus vaporized placebo, and 3) double placebo. The three arms are shortly called 1) vaporized cannabis; 2) dronabinol; 3) placebo. After randomization, each patient will receive study medication at home for 8 weeks after which they will be tapered off of investigational treatments over two weeks. The three study periods include: i) Titration (weeks 0-4); ii) Treatment (weeks 5-8); iii) Tapering (Weeks 9-10). During the titration period, patients will undergo titration of vaporized medication from 4 puffs to 18 puffs, or oral medication from 5 mg qd to 10 mg tid per day. Subjects will be dropped from the study by the end of Week 4 if they are unable to tolerate the minimum amounts of medication described above, and replaced by another volunteer. During the treatment period, subjects will be expected to consume the amount of study medication that they titrated themselves up to by the end of week 4. During the tapering period, patients will slowly withdraw from medication over two weeks. During treatment at home (weeks 1-8), patients will maintain a paper daily diary to record their intake of study medications, and breakthrough pain medications, as well as pain relief measurements. Outcome measure (such as self-report forms and neuropsychological testing) will be collected during the six study visits. If participating in Driving Simulation, subjects with driver licenses will be scheduled for two experimental visits.

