4.1.1 Primary analysis

The primary analysis will be the comparison of self-reported pain intensity between arm A and arm B. An intent-to-treat analysis will be performed on data from participants who complete baseline. Data transformation (e.g., log10, square root) may be performed to improve distribution normality as appropriate. Response profiles analysis will be performed if the trend of pain intensity over time is not linear. We will compare different covariance pattern models (e.g., unstructured, compound symmetry) based on AIC and identify a covariance model with the best fit to our data. This is a randomized controlled trial so that we can remove main group effect with assumptions about equal mean responses (i.e., pain scores) at baseline for the three treatment arms. Weekly or biweekly average of pain intensity from the daily diary will be calculated as a primary outcome. Time will be treated as a factor with 6 levels (i.e., baseline, weeks 1, 3, 5, 7, 8), and the mean response profiles will be compared between the arms. The treatment effect over time will be assessed by the significance of the treatment arm x time interaction using Wald test. Also, average change at the treatment period (weeks 5-8) from baseline will be compared between the groups. (Aim 1)

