4.2.4 Comparison of driving performance between treatment arms

The driving simulation assessments will be conducted in the substudy. (1) Driving measurements (standard deviation of lateral deviation (SDLP) for lane tracking and coherence for car following) following 8 weeks of study medication administration will be compared between treatment arms using ANOVA, to determine whether driving skills will be different after stable cannabis treatment. Acute cannabis effects will be then tested using a covariance pattern model (e.g., unstructured model) including fixed effects of treatment arm, time (minutes), and their interaction. (2) We will also include terms for pain (separately using intensity and relief), its interaction with treatment, and time too, the latter to test for recovery of the cannabis effect back to the Hour 1 baseline level. (3) The correlation (Pearson or Spearman, as appropriate) between blood $\Delta 9$ -THC and each of SDLP and coherence will be estimated at each hour using a 95% confidence interval applied to the Fisher Z-transformation, then back-transformed. Secondary analyses will use independent t-tests or Wilcoxon rank sum tests to compare differences between the means of each of coherence and SDLP for high and low blood $\Delta 9$ -THC levels split at 7 ng/ml. (Aim 3)

4.3 Exploratory analysis:

4.3.1 We will assess the association of daily pain intensity and the dose of treatment (mean daily number of puffs or pills) using a mixed-effects model including fixed effects of dose, treatment regimen, time (i.e., day or week), and dose x treatment regimen interaction, and subject-specific random effect. A significant interaction indicates the association of the dose and pain intensity differs in the three treatment arms. Use of breakthrough pain medication will be then included in the model to remove its confounding effect if it's present. A Non-significant interaction will be removed from the models.

- 4.3.2 Cumulative distributions of maximal pain reduction from baseline among treatment groups will be compared using Kolmogorov-Smirnov tests. This test (nonparametric) will indicate if a given treatment is likely to produce more overall pain reduction than another treatment regimen and takes into account an expected delay in effects of dronabinol compared to whole plant cannabis.

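### SAP 4.3.1: with only a subject random effect, the daily dose-pain tests are likely anti-conservative if pain is serially correlated, and self-titrated dose can give a positive slope when dose does nothing

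*SAP*

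**What the plan says.** SAP 4.3.1 opens the exploratory analyses: "We will assess the association of daily pain intensity and the dose of treatment", with dose defined as "mean daily number of puffs or pills". The model contains "fixed effects of dose, treatment regimen, time (i.e., day or week), and dose x treatment regimen interaction, and subject-specific random effect". A significant interaction is taken to mean that the association differs between arms; a non-significant one is dropped. Breakthrough medication is the only confounder named. The window over which daily dose is averaged is not given, and time may be day or week.

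For the primary model, SAP 4.1.1 does address within-person correlation: "We will compare different covariance pattern models (e.g., unstructured, compound symmetry) based on AIC". Section 4.3.1 has no such step.

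On how dose arises, Protocol section 15 says that "participants will titrate to effect and in essence use the minimum amount of medicinal cannabis needed to obtain relief from pain". Protocol section 9 gives the range: "The vaporized cannabis will be titrated from a minimum of 4 puffs to a maximum of 18 puffs per day". Table 1 there caps daily puffs at 4, 8 and 12 in weeks 1-3 and at 18 from week 4. For weeks 5-8, SAP section 1 says that "subjects will be expected to consume the amount of study medication that they titrated themselves up to by the end of week 4".

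**The concern.** There are two separate problems.

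**Precision.** A single random intercept treats any two days of one person as equally correlated. Diary pain on neighbouring days is usually more alike than pain weeks apart. When the covariate also moves slowly, the model counts more independent information about the slope than the data hold, and its standard error is too small.

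**Direction.** Treatment is randomised but dose within an arm is not. If people take more when pain is worse, the slope combines the effect of dose on pain with the effect of pain on dose. The second part is positive and can hide a benefit or reverse its sign.

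At stake is whether a significant dose slope, or a significant dose by regimen term, can be taken at face value when the exploratory results are reported.

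**Working it through.** **1. The plan's own figure.** Section 4.3.1 states none. The SAP's only power figure (5.1) is 80% at d = 0.54 with 33 per arm and d = 0.58 with 29. The longitudinal slope formula reproduces it: m = 2(1.960 + 0.842)²(1 − r) / [SS × (d/8)²]. Visit times 0, 1, 3, 5, 7, 8 have mean 4, so SS = 16 + 9 + 1 + 1 + 9 + 16 = 52. With between-visit correlation r = 0.5 (assumed), the numerator is 7.849. Then 7.849/(52 × 0.0675²) = 33.1 and 7.849/(52 × 0.0725²) = 28.7. That figure concerns arm by time and says nothing about the dose slope.

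**2. Inputs.** From the documents: 33 completers per arm, 3 × 33 = 99 people; 8 × 7 = 56 diary days; Table 1 puff caps; range 4-18 puffs; 5% level (two-sided assumed). Assumed: between-person pain SD 1.5, day-to-day SD 1.2, first-order autoregressive pain with correlation ρ, each person's plateau uniform on 4-18 puffs, and feedback of 0.5 to 2 puffs per pain point where feedback is studied. The true dose effect is zero unless stated.

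**3. Size of the standard-error problem by formula.** If dose within a person has day-to-day correlation φ, the true variance of the slope is roughly V = (1 + ρφ)/(1 − ρφ) times the model's. A nominal 5% test then rejects with probability 2Φ(−1.96/√V).

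- ρ = 0.5, φ = 0.7: V = 1.35/0.65 = 2.08; 1.96/√2.08 = 1.36; rejection 17%.
- ρ = 0.7, φ = 0.9: V = 1.63/0.37 = 4.41; 1.96/√4.41 = 0.93; rejection 35%.
- φ = 0 (dose independent from day to day): V = 1; rejection 5%.

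**4. By simulation, no true effect.**

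| ρ | Slope, generic persistent dose | Slope, Table 1 caps then held plateau | Interaction, Table 1 caps then held plateau |
|---|---|---|---|
| 0 | 5-6% | about 5% | about 5% |
| 0.3 | 10-11% | 14-18% | 18-20% |
| 0.5 | 16-19% | 24-25% | 31-33% |
| 0.7 | 26-28% | 33-35% | 49-57% |

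In the generic runs the model standard error is 0.80-0.84, 0.67-0.73 and 0.56-0.57 of the true one at ρ = 0.3, 0.5 and 0.7. Unmodelled differences in personal pain trend (SD 1.5 over 8 weeks, assumed) give 21-28% on their own.

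Benign cases for the slope: 4% when dose varies independently by day (ρ = 0.5-0.7), and 6-8% when pain and dose are both reduced to weekly means.

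**5. Direction.** Let pain have SD 1, and let dose equal g × pain plus other variation of SD 1. The regression of pain on dose then has slope g/(g² + 1), although dose does nothing. For g = 0.1, 0.2, 0.3 this is 0.10, 0.19, 0.28. In puffs and pain points, with feedback of 0.5-2 puffs per point:

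- same-day dose: +0.28 to +0.40 per puff, significant in all runs;
- same-day dose, no feedback in weeks 5-8: +0.13 to +0.25, significant in all runs;
- weekly-mean dose: about +0.01 to +0.28, the smallest value (12% rejection) with ρ = 0 and dose held;
- whole-study mean dose: +0.19 to +0.39;
- true benefit of −0.05 per puff: the same-day slope is still +0.08 to +0.34.

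**6. Interaction under feedback.** With 3 × 33 people, 56 days and dose rising 0.2 SD per SD of pain in every arm, each arm's slope is +0.19 to +0.24 but the mean difference between arms is about 0.00. The interaction test rejects 5% when neither series is autocorrelated, and 23-46% when both are. The excess is the standard-error problem, not a bias.

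**7. What repairs achieve.** Subject-clustered errors bring the slope test to 4-7% and the interaction to 8-9%. They do not remove the bias in section 5. Previous-day dose with previous-day pain gives a slope within about 0.005 of zero if feedback runs through all 8 weeks, but leaves about +0.02 to +0.09 if dose is held in weeks 5-8.

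**The case against.** The strongest case on the other side is that the plan promises little here and that several tempting inferences go beyond it.

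- **A same-day dose model.** A reader might infer one, but the SAP leaves the window undefined. This stands. It matters for the standard error (near nominal on weekly means) and for the size of the bias, though the average slope under feedback was positive in every window tried.
- **Standard errors certainly too small.** This needs serially correlated pain or unmodelled personal trends, together with persistent dose. The documents give no autocorrelation, and a subject-specific effect could be read to include a slope. This stands as a condition. Persistence of dose is not mere assumption, however: the weekly caps and the held dose imply it.
- **Held dose limits feedback.** This is true for weeks 5-8, and it shrinks the direction problem without removing it. It also makes dose more persistent, which worsens the precision problem.
- **A wrong-signed interaction.** A reader might extend the sign problem to dose by regimen. All arms titrate under double-dummy blinding, and common feedback cancels from the difference, so this is not supported.
- **A planned causal claim.** The SAP speaks of an association under an exploratory heading. It does not announce a dose-response conclusion.
- **Replacing dose by the previous day's dose.** This would fit the design poorly. The protocol (section 18) describes herbal cannabis as quick in onset and short in action, and its diary rule is that "subjects will be asked to enter data into paper diary within a one-to-two hour window following dosing of study and breakthrough medications". The previous day's puffs could miss the effect of interest.

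**Conclusion.** The point holds in conditional form. As written, the model has nothing beyond a subject random effect to handle correlation across up to 56 days. If daily pain is serially correlated at 0.3-0.7 (assumed), nominal 5% tests reject in about 10-35% of runs for the slope and 18-57% for the interaction. With no serial correlation they are correct.

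Self-titration can make the slope positive when dose has no effect. Its size depends on the assumed feedback and on the averaging window. Other dosing behaviour, such as dose limited by poor tolerability, could change the sign of the bias.

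No primary or secondary endpoint and no power figure depends on 4.3.1. This is a cheap improvement to an exploratory analysis, not a threat to the trial's main result.

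**What to change.** Amend SAP 4.3.1 to:

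1. State the window over which dose is averaged and whether the unit of analysis is the day or the week.
2. Add a first-order autoregressive residual to the random intercept, or choose the covariance by AIC as in 4.1.1, or use subject-clustered robust errors. Clustered errors also allow for personal trends; with them the interaction test remained slightly liberal (8-9%) in these runs.
3. Split dose into each person's mean and the deviation from it, and report both slopes.
4. State that neither slope is to be read as a causal dose-response effect, because dose is chosen in response to pain.
5. Optionally add, as a sensitivity analysis and not a replacement, a model with the previous day's dose and the previous day's pain, noting that some bias can remain.

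The cost is a few lines of text and code, a little more modelling work and wider intervals. No new data are needed.

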4.1 Primary endpoint

The primary outcome will be self-reported daily average numerical pain intensity during the past 24 hours. The comparisons are following as following: 1) primary comparison: arm A vs. arm B; 2) secondary comparison: arm A vs. arm C; exploratory comparison: arm B vs. arm C. Since the three comparisons have different levels of importance, no correction will be done for multiple comparisons.

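### SAP 4.3.2 reads a Kolmogorov-Smirnov test on maximal pain reduction as evidence of greater overall reduction, which a peak-response measure cannot show

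*SAP*

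**What the plan says.** SAP 4.3.2 falls under "4.3 Exploratory analysis". It specifies: "Cumulative distributions of maximal pain reduction from baseline among treatment groups will be compared using Kolmogorov-Smirnov tests". Two claims follow. The first is how the result will be read: "This test (nonparametric) will indicate if a given treatment is likely to produce more overall pain reduction than another treatment regimen". The second is why the maximum was chosen: the test "takes into account an expected delay in effects of dronabinol compared to whole plant cannabis".

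SAP 4.3.2 gives no unit for the maximum (day, weekly average or visit), no time window, no analysis population and no direction for the test. Other sections define the pain variable in two ways. SAP 4.1 says: "The primary outcome will be self-reported daily average numerical pain intensity during the past 24 hours". SAP 4.1.1 says: "Weekly or biweekly average of pain intensity from the daily diary will be calculated as a primary outcome". SAP 4.1.1 also plans a mean-based summary: "average change at the treatment period (weeks 5-8) from baseline will be compared between the groups". SAP 4.3.2 refers to none of these.

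**The concern.** The largest reduction over many noisy ratings is an extreme value. It equals the person's mean reduction plus an amount that grows with the scatter of the ratings. Two arms with the same average pain but different day-to-day scatter will therefore differ in maximal reduction. The K-S test is sensitive to such a difference, and a two-sided version gives no direction by itself.

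At stake is the published reading. A significant result would be reported as more overall relief when it may show only that one arm had better single days. The same mechanism can hide a real difference in mean pain if the less effective arm is the more variable one.

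**Working it through.** **Inputs from the documents.** 40 randomised per arm and 16% dropout (SAP 2.2 and 5.1): 40 × 0.84 = 33.6, taken as 33. Eight weeks of home treatment (SAP 1) give at most 8 × 7 = 56 diary days. The significance level is 5% (SAP 5.1), taken as two-sided.

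**The plan's own figure.** The SAP gives no figure for the K-S analysis. Its general figure is 80% power at d = 0.54 (33 per arm) and d = 0.58 (29 per arm). The slope formula for a time-by-treatment interaction is d = 8 × (1.96 + 0.84) × √[2(1 − ρ)/(n × Sxx)]. Times 0, 1, 3, 5, 7, 8 have mean 4, so Sxx = 16 + 9 + 1 + 1 + 9 + 16 = 52. The SAP does not state ρ. With ρ = 0.5 the formula gives d = 0.541 for n = 33 and 0.577 for n = 29, so both figures reproduce under that assumption.

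**Assumed, because the documents give no values.** 0-10 integer scores, 7-day baseline, baseline mean 6 (SD 1.3), mean reduction 1.0 in both arms with between-person SD 1.3, and daily within-person SD 1.0 in one arm against 1.0 to 2.0 in the other. Variants used between-person SD 1.5, unbounded scores, or a day-to-day correlation of 0.5. Each setting had 1,500 to 3,000 simulated trials.

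**Why the maximum moves.** Per person, maximal reduction = baseline mean − lowest rating. With 56 unbounded ratings and no treatment effect it averages about 2.3 daily SDs: 2.3 points at SD 1.0, 2.3 × 1.3 = 3.0, 2.3 × 1.5 = 3.4 to 3.5, and 2.3 × 2.0 = 4.6. None of this is pain relief.

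**Rejection rates with equal mean pain, 33 per arm:**

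| Daily SD | K-S, daily maximum | K-S, maximum of weekly averages |
|---|---|---|
| 1.0 v 1.0 | about 2% | 2-3% |
| 1.0 v 1.3 | 15-20% | 3-5% |
| 1.0 v 1.5 | 45-55% | 4-8% |
| 1.0 v 2.0 | 96-99% | 7-25% |

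The weekly column runs from independent days with five weeks to day-to-day correlation 0.5 with eight weeks. Biweekly averages with independent days gave 2.5%, 2.9% and 5.7% at SD 1.3, 1.5 and 2.0. The daily column depends on the other assumptions too. At SD 1.0 v 1.5, unbounded scores with between-person SD 1.3 gave 66%. No effect in either arm with between-person SD 0.8 gave 83%, with mean maximal reductions of 2.3 and 3.4 points.

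**Mean reduction over weeks 5-8, same settings.** Wilcoxon rank-sum and the t-test reject in about 4-6% of trials at every SD ratio.

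**Diary days, equal SDs, daily maximum.** Dropout of 16% v 16% gives 2%, 8% v 24% gives 2%, and 5% v 40% gives 3%. Diary completeness of 95% v 60% gives 3%. If everyone in one arm had 28 days against 56, the rate is 4%. It reaches 15% at 14 days and 41% at 7 days.

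**When a true difference exists.** Take d = 0.54 with SD of change 1.3: 0.54 × 1.3 = 0.70 points. With equal daily SDs, K-S on the daily maximum detects it in 21-23% of trials, K-S on the weeks 5-8 mean in 30%, and a t-test on that mean in 53%. If the less effective arm has daily SD 1.5 against 1.0, K-S on the daily maximum rejects in only 6%, while the t-test on mean reduction still rejects in 55%.

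**The case against.** The strongest reply is that the high rates depend on two things the documents do not state. The first is the unit. The only processed pain outcome in the SAP is a weekly or biweekly average, and on that reading the inflation mostly disappears. The second is unequal variability. Neither document gives a within-person SD or evidence that it differs by arm. Protocol section 18 describes faster onset and shorter action for herbal cannabis, and section 7 reports longer-lasting analgesia with dronabinol. Those are differences within a day, though. The rating covers a 24-hour average, and Protocol Table 1 has both routes reaching three administrations a day. Both replies stand. They make the size conditional and rule out any claim that the test would favour vaporized cannabis.

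Three stronger readings are tempting, and none is supported:
- A reader might infer that the statistic measures only variability and the number of diary days. It also responds to a true mean difference, and it keeps its error rate when the arms have equal scatter and equal follow-up.
- A reader might infer that uneven dropout would drive the result. At 8% against 24% the rejection rate stays near 2%.
- A reader might infer that the trial's main conclusion is exposed. The analysis is labelled exploratory, and the primary comparison in SAP 4.1.1 does not use it.

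Peak response is also a legitimate question in its own right. What the reply does not rescue is the sentence that equates the test with overall pain reduction.

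**Conclusion.** The point holds for the interpretation rule in SAP 4.3.2. A K-S test on a maximum shows that the distributions of peak response differ. It cannot by itself show more overall pain reduction, whichever unit is meant.

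The error is potentially large only if the maximum is over daily ratings and day-to-day variability differs by arm. Under those assumed conditions, false readings occur in about 15-20%, 45-55% and 96-99% of trials at SD 1.0 against 1.3, 1.5 and 2.0. On weekly averages they are about 3-8% up to SD 1.5 and 7-25% at SD 2.0. The SD ratios are illustrations, not estimates for this trial.

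The delayed-onset rationale does not require a maximum. If the delay is in hours, the 24-hour rating already covers it. If it is in weeks, the weeks 5-8 window follows titration.

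**What to change.** Base any statement about overall pain reduction on each person's mean reduction from baseline over weeks 5-8. Show it as cumulative distribution curves by arm and compare the arms by Wilcoxon rank-sum. State the population and how participants without ratings in weeks 5-8 are handled.

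If maximal reduction is kept, compute it on weekly averages, state the window and population, and describe the K-S result only as a difference in the distribution of peak response. Delete the sentence that reads it as overall reduction.

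The cost is SAP wording, since the diary data are already collected. The downside is some overlap with the weeks 5-8 comparison planned in SAP 4.1.1.
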